#### 15.1.5.2. Treatment-by-pooled Region Interaction

The effect of pooled region on the primary efficacy variable for the ITT population is to be investigated using the same MMRM as described in Section 15.1.3 Primary Analysis of Primary Efficacy Variable with the addition of a treatment-by-pooled region interaction effect.

The interaction is to be further explored by doing subgroup analysis for each pooled region if the effect is found to be statistically significant.

#### 15.1.5.3. Alternative Combined Score Weighting

The CS provides equal weighting (a maximum score of 3 each) for the contribution of the symptoms and the rescue medication use.

Document: TH005 SAP Version 2.docx  
Author: [name]

Version Number: 2.0  
Version Date: 24MAR2017

Template No: CS\_TP\_BS016 – Revision 3  
Effective Date: 01May2012

Reference: CS\_WI\_BS005

Copyright © 2012 Quintiles Transnational Corp. All rights reserved.  
The contents of this document are confidential and proprietary to Quintiles Transnational Corp. Unauthorized use, disclosure or reproduction is strictly prohibited.

Two alternative CS are to be calculated for sensitivity testing of the impact of different weighting of TRSS and RMS as follows:

The TRSS (0 to 24) and the RMS (0 to 3) is to be combined for analysis of the alternative primary variable as follows:

- Alternative 1 CS (ALT1 CS) =  $(4/3 * \text{TRSS}/8) + (2/3 * \text{RMS})$

Mean ALT1 CS is to be calculated in BAE, PAC1, PAC2 and PAC3 by taking the mean ALT1 CS over all the days with complete data for the BAE and each PAC period.

- Alternative 2 CS (ALT2 CS) =  $(2/3 * \text{TRSS}/8) + (4/3 * \text{RMS})$

Mean ALT2 CS is to be calculated in BAE, PAC1, PAC2 and PAC3 by taking the mean ALT2 CS over all the days with complete data for the BAE and each PAC period.

A third and fourth alternative CS is to be calculated for sensitivity testing of the impact of increased weighting of oral corticosteroid use.

An alternative RMS (ALT RMS) for the purpose of testing the impact of oral corticosteroid use is to be evaluated as follows:

- ALT RMS = 0; no allergy rescue medication used per day
- ALT RMS = 0.5; at least one dose of antihistamine eye drops used per day
- ALT RMS = 1; at least one dose of oral antihistamine used per day
- ALT RMS = 2; at least one dose of intranasal corticosteroid used per day
- ALT RMS = 6; at least one dose of systemic corticosteroid used per day

The TRSS (0 to 24) and the ALT RMS (0 to 6) is to be combined for analysis of the alternative primary variable as follows:

- Alternative 3 CS (ALT3 CS) =  $\text{TRSS}/8 + \text{ALT RMS}/2$

This formula maintains equal weighting (a maximum score of 3 each) for the contribution of the symptoms and the rescue medication use and maintains the maximum score of 6.

Mean ALT3 CS is to be calculated in BAE, PAC1, PAC2 and PAC3 by taking the mean ALT3 CS over all the days with complete data for the BAE each PAC period.

- Alternative 4 (ALT4 CS) =  $\text{TRSS}/8 + \text{ALT RMS}$

This formula ensures that the use of oral corticosteroids results in a combined score of at least 6 even if no symptoms are present; the maximum score is 9.

Mean ALT4 CS is to be calculated in BAE, PAC1, PAC2 and PAC3 by taking the mean ALT4 CS over all the days with complete data for the BAE and each PAC period.

A point estimate and two-sided 95% confidence interval for the difference in adjusted means of ALT1 CS, ALT2

Document: TH005 SAP Version 2.docx

Author: [name]

Version Number:

2.0

Version Date:

24MAR2017

Template No: CS\_TP\_BS016 – Revision 3

Effective Date: 01May2012

Reference: CS\_WI\_BS005

Copyright © 2012 Quintiles Transnational Corp. All rights reserved.

The contents of this document are confidential and proprietary to Quintiles Transnational Corp. Unauthorized use, disclosure or reproduction is strictly prohibited.

---

CS, ALT3 CS and ALT4 CS between the active treatment groups and placebo is to be calculated using the same MMRM as described in Section 15.1.3 Primary Analysis of Primary Efficacy Variable.

### **15.1.6. NORMALITY AND HOMOGENEITY OF PRIMARY EFFICACY VARIABLE**

The residuals from the primary efficacy MMRM, sensitivity analysis MMRM as well as supportive primary efficacy analysis MMRM are to be visually checked for normality and homogeneity of variance. Normality is to be examined by normal probability plots, while homogeneity of variance is to be assessed by plotting the residuals against the predicted values for the model. Any deviation from either assumption may result in further analysis using non-parametric analysis of the primary efficacy variable.

## **15.2. SECONDARY EFFICACY**

The secondary efficacy analyses are to be performed for the ITT population.

The secondary efficacy analyses are to be prioritised in order of importance as outlined below.

### **15.2.1. SECONDARY EFFICACY VARIABLES & DERIVATIONS**

#### **15.2.1.1. Mean Total Rhinoconjunctivitis Symptom Score**

The daily TRSS is to be derived as described in Section 15.1.1: Primary Efficacy Variable & Derivation.

The means of the daily TRSS for the BAE, PAC1, PAC2 and PAC3 periods are to be calculated over all days with complete data.

##### Analysis of Mean Total Rhinoconjunctivitis Symptom Score

A point estimate and two-sided 95% confidence interval for the difference in adjusted means between the active treatment groups and placebo is to be calculated using the same MMRM as described in Section 15.1.3 Primary Analysis of Primary Efficacy Variable.

- The treatment difference corresponding to the PAC3 period is to be utilised for the secondary analysis
- The treatment difference corresponding to the PAC1 and PAC2 periods are to be utilised as exploratory analyses

Observed and change from Baseline values are to be summarised by descriptive statistics for the PAC1, PAC2 and PAC3 periods by treatment group.

#### **15.2.1.2. Mean Component Scores of Total Rhinoconjunctivitis Symptom Score**

The TRSS consists of two components:

- Total Nasal Symptom Score (TNSS)

---

Document: TH005 SAP Version 2.docx  
Author: [name]

Version Number: 2.0  
Version Date: 24MAR2017

Template No: CS\_TP\_BS016 – Revision 3  
Effective Date: 01May2012

Reference: CS\_WI\_BS005

---

The TNSS is the sum of four individual nasal symptoms: runny nose, sneezing, blocked nose, and itchy nose. The TNSS will have a range of 0-12. The TNSS is to be calculated on each day as follows:

TNSS = Runny Nose + Sneezing + Blocked Nose + Itchy Nose.

Mean TNSS is to be calculated for the BAE, PAC1, PAC2 and PAC3 periods over all days with complete data.

- Total Non-nasal Symptom Score (TNNSS)

The TNNSS is the sum of four individual non-nasal symptoms: itchy eyes, watery eyes, red eyes and itchy ear/palate.

The TNNSS will have a range of 0-12. The TNNSS is to be calculated on each day as follows:

TNNSS = Itchy Eyes + Watery Eyes + Red Eyes + Itchy Ear/Palate.

Mean TNNSS is to be calculated for the BAE, PAC1, PAC2 and PAC3 periods over all days with complete data.

#### Analysis of Mean Component Scores of Total Rhinoconjunctivitis Symptom Score

For both the TNSS and TNNSS a point estimate and two-sided 95% confidence interval for the difference in adjusted means between the active treatment groups and placebo is to be calculated using the same MMRM as described in Section 15.1.3 Primary Analysis of Primary Efficacy Variable.

- The treatment difference corresponding to the PAC3 period is to be utilised for the secondary analysis
- The treatment difference corresponding to the PAC1 and PAC2 periods are to be utilised as exploratory analyses

Observed and change from Baseline values are to be summarised by descriptive statistics for the PAC1, PAC2 and PAC3 periods by treatment group.

#### 15.2.1.3. Mean Rescue Medication Score

The daily RMS is to be derived as described in Section 15.1.1: Primary Efficacy Variable & Derivation.

The means of the daily RMS for the BAE, PAC1, PAC2 and PAC3 periods are to be calculated over all days with complete data.

#### Analysis of Rescue Medication Score

A point estimate and two-sided 95% confidence interval for the difference in adjusted means between the active treatment groups and placebo is to be calculated using the same MMRM as described in Section 15.1.3 Primary Analysis of Primary Efficacy Variable.

- The treatment difference corresponding to the PAC3 period is to be utilised for the secondary analysis
- The treatment difference corresponding to the PAC1 and PAC2 periods are to be utilised as exploratory analyses

Observed and change from Baseline values are to be summarised by descriptive statistics for the PAC1, PAC2 and PAC3 periods by treatment group.

---

Document: TH005 SAP Version 2.docx  
Author: [name]

Version Number: 2.0  
Version Date: 24MAR2017

Template No: CS\_TP\_BS016 – Revision 3  
Effective Date: 01May2012

Reference: CS\_WI\_BS005

---

#### 15.2.1.4. Clinical Global Impression of Change in Rhinoconjunctivitis Symptoms

During the Follow-up Visit (Visit 5) subjects are to complete a Clinical Global Impression (CGI) of change in Rhinoconjunctivitis symptoms.

Subjects are to rate their overall allergy symptoms at the end of the study relative to Baseline on a 7-point scale as follows:

0 = Very much better

1 = Moderately better

2 = A little better

3 = Unchanged

4 = A little worse

5 = Moderately worse

6 = Very much worse

The following additional categories of global impression are to be derived:

- Moderately or very much better
- Any improvement (a little better, moderately better or very much better)
- No change (unchanged)
- Any worsening (a little worse, moderately worse or very much worse)

#### Analysis of Clinical Global Impression of Change

The frequency (n) and percentage (%) of subjects in each category of CGI is to be presented.

A p-value for the difference in CGI between each HDM-SPIRE treatment group and placebo across all 7 categories is to be calculated using the Cochran-Mantel-Haenszel (CMH) row mean score differ.

The frequency (n) and percentage (%) of subjects in each of the following derived categories is to be presented

- Moderately or very much better
- Any improvement
- No change
- Any worsening

A Chi-square test is to be used to calculate a p-value for the difference in each derived CGI category between each HDM-SPIRE treatment group and placebo.

---

Document: TH005 SAP Version 2.docx

Author: [name]

Version Number:

2.0

Version Date:

24MAR2017

Template No: CS\_TP\_BS016 – Revision 3

Effective Date: 01May2012

Reference: CS\_WI\_BS005

Copyright © 2012 Quintiles Transnational Corp. All rights reserved.

The contents of this document are confidential and proprietary to Quintiles Transnational Corp. Unauthorized use, disclosure or reproduction is strictly prohibited.

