### 3.2.2 Secondary Efficacy Variables

The secondary efficacy variables are

- Clinical Global Impression of Change in Rhinoconjunctivitis Symptoms for the HDM-SPIRE treatment groups compared with placebo at the end of study.
- Mean TRSS in the HDM-SPIRE treatment groups compared with placebo during the

VERSION FINAL 4.0 CONFIDENTIAL PAGE 23 OF 92

- PAC3 period.
- Mean component scores of the TRSS (nasal and non-nasal) in the HDM-SPIRE treatment groups compared with placebo during the PAC3 period.
- Mean RMS in the HDM-SPIRE treatment groups compared with placebo during the PAC3 period.
- Mean Rhinoconjunctivitis Quality of Life Questionnaire (RQLQ) score in the HDM-SPIRE treatment groups compared with placebo at the end of the PAC3 period.
- Number of days subjects in the HDM-SPIRE treatment groups have no moderate or severe RSS symptoms without rescue medication usage compared with placebo during the PAC3 period.

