### 5.7 Randomisation

Subjects who successfully complete Period 1 Screening and continue to meet the study entry criteria at the end of the BAE, will be randomised to receive placebo or one of the HDM-SPIRE regimens. The Randomisation Schedule will be produced by a computer-generated algorithm by HMD Clinical.

Subjects will be randomised on an equal basis (i.e. 1:1:1:1) to placebo and each of the 3 HDM-SPIRE treatment groups.

VERSION FINAL 4.0 CONFIDENTIAL PAGE 35 OF 92

Randomisation will be stratified according to the following criteria:

DATE 01 APRIL 2015

- Current history of asthma (present or absent)
- Mean TRSS during BAE ( $<16, \ge 16$ )

Study medication packs will be assembled in accordance with the Randomisation Schedule. An interactive response technology (IRT) system will be used to allocate study medication packs to subjects, according to the randomisation and stratification schema. The Investigator or designee will also record the Subject Screening Number against the allocated randomised study pack on the Drug Accountability Record.

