## 7.5.3.2.3 Clinical Global Impression of Change in Rhinoconjunctivitis Symptoms

An evaluation of the number of subjects in each category of the Clinical Global Impression of Change in Rhinoconjunctivitis Symptoms will be presented. Global impression of Change will be analysed using the Cochran-Mantel-Haenszel test.

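### The CGI tests in SAP 15.2.1.4 name no strata although randomisation is stratified by asthma and baseline TRSS: valid, but a small free gain is left unused

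*SAP*

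**What the plan says.** Protocol 5.7: "Randomisation will be stratified according to the following criteria", followed by current asthma (present or absent) and "Mean TRSS during BAE" (<16, ≥16). That makes 2 × 2 = 4 cells. SAP 9 and 10 confirm that both factors are held on the Randomization (RAND) eCRF.

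Protocol 7.5.3.2.3: "Global impression of Change will be analysed using the Cochran-Mantel-Haenszel test". No strata are given.

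SAP 15.2.1.4: for each active arm against placebo, the p-value across the seven categories "is to be calculated using the Cochran-Mantel-Haenszel (CMH) row mean score differ". For the four grouped categories derived from the seven-point scale, the section says: "A Chi-square test is to be used to calculate a p-value for the difference in each derived CGI category". Neither sentence names a stratum or covariate.

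SAP 7.1 lists the adjustment factors and leaves their use to each analysis section; the CGI section uses none. Every other secondary endpoint in SAP 15.2 is adjusted. TRSS and its components, RMS, well days and the asthma symptom score reuse the primary MMRM (asthma status, gender, pooled region, baseline score), and RQLQ uses an ANCOVA with the same kinds of term.

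**The concern.** Stratified randomisation balances the arms on asthma and baseline severity. If those factors also predict the outcome, the true variance of the between-arm difference is smaller than a test that ignores them assumes. Such a test rejects less often than its nominal level under the null and has less power under the alternative.

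A link between the strata and CGI is plausible but not quantified in the documents. CGI asks subjects to rate their symptoms relative to Baseline, and one stratum is baseline symptom severity. Protocol 1.2 and 1.3.1 report post-hoc TH002 analyses that suggested response differed by baseline severity, although those concern treatment response in an exposure chamber, not CGI.

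What is at stake is a little efficiency on one secondary endpoint, and an analyst choice that is better written down before unblinding: the SAP names a CMH test and does not say whether it is stratified.

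**Working it through.** **1. The plan's own figure.** The only power statement (Protocol 7.2, SAP 3.2) is for the primary combined score: difference 0.32, SD 0.986, two-sided 5%, 80% power.

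- n per group = 2 × (1.960 + 0.842)² × 0.986² / 0.32² = 149.04, rounded up to 150. This reproduces the plan.
- Power at 150: 0.32 / (0.986 × √(2/150)) = 2.811; Φ(2.811 − 1.960) = 80.3%.

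Nothing in this point changes these figures. They are not a power statement for CGI, so the 80% below is only an illustrative start.

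**2. Formula with balanced strata.** Let R² be the share of CGI variance explained by the strata (assumed; not in the documents). With arms balanced within strata, the unstratified statistic has standard deviation √(1 − R²) instead of 1.

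- True size of a nominal 5% unstratified test: 2 × Φ(−1.960/√(1 − R²)).
- If the unstratified test has 80% power, its mean is 1.960 + 0.842 × √(1 − R²). The stratified statistic divides this by √(1 − R²) and has standard deviation 1, so its power is Φ(0.842 + 1.960/√(1 − R²) − 1.960).

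| R² | 1.960/√(1 − R²) | Size, unstratified | Power, unstratified | Power, stratified |
|---|---|---|---|---|
| 0% | 1.960 | 5.0% | 80% | 80.0% |
| 2% | 1.980 | 4.8% | 80% | Φ(0.862) = 80.6% |
| 5% | 2.011 | 4.4% | 80% | Φ(0.893) = 81.4% |
| 10% | 2.066 | 3.9% | 80% | Φ(0.948) = 82.8% |

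**3. Simulation on a seven-point scale.** The assumptions, none from the documents, are:

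- a latent normal CGI with placebo category cut-points at cumulative 12, 30, 52, 80, 91 and 97%;
- TRSS ≥16 in 50% of subjects and asthma in 30%;
- a treatment effect of 0.324 latent SD, borrowed from 0.32/0.986;
- a latent shift s for each stratification factor;
- exact balance within cells of 52, 22, 52 and 22 per arm (148 per arm after rounding 150), and 20,000 runs.

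The factor variances add up to s² × (0.5 × 0.5 + 0.3 × 0.7) = 0.46 s², so s = 0.2, 0.4 and 0.6 correspond to a latent R² of about 1.8%, 6.9% and 14.2%.

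| s | Row-mean-score size, unstratified / stratified | Row-mean-score power, unstratified / stratified | Any improvement: power, chi-square / stratified CMH |
|---|---|---|---|
| 0 | 5.1% / 5.1% | 76.8% / 76.7% | 59.9% / 59.9% |
| 0.2 | 4.9% / 5.1% | 76.1% / 76.5% | 59.5% / 59.6% |
| 0.4 | 4.3% / 5.0% | 74.1% / 76.1% | 57.4% / 58.2% |
| 0.6 | 3.5% / 4.9% | 71.0% / 75.7% | 53.6% / 56.7% |

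Both approaches agree. Ignoring the strata does not inflate the error rate, the loss grows with the strength of the strata, it is smaller for the derived category, and stratifying costs about 0.1 point or less when the strata explain nothing.

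**The case against.** The best defence is that nothing is broken. The row-mean-score statistic on a single table is an accepted ordinal test for a seven-point scale, and a chi-square on a two-by-two table is valid. A reader might infer that a CMH test without strata is a misuse, or that the p-values are too small. Neither follows: the error rate is at or below nominal. This part of the defence stands in full.

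A reader might also give CGI more weight because it comes first in Protocol 3.2.2. That is a plain list. Protocol 7.5.3.2 and SAP 15.2 say that their order reflects importance, and there CGI comes third and fourth. It is also outside the step-down procedure of SAP 7.4, which covers the primary analysis only.

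Nor are the strata the only variables available for adjustment. Gender, pooled region, asthma status and the continuous BAE scores are all recorded. The primary MMRM uses continuous baseline CS and three-level asthma status, not the TRSS cut at 16, so stratifying CGI by the randomisation cells follows the design but does not copy the MMRM.

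Finally, a reader might compute a larger gain from Φ(2.80/√(1 − R²) − 1.96), which gives 80.8%, 82.0% and 84.0%. That formula treats the unstratified test as correctly sized, as under simple randomisation. With balanced strata it overstates the gain.

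What remains is that no section supplies strata for CGI, the other secondary endpoints are adjusted, and the change is close to free.

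**Conclusion.** The point holds as a low-priority free improvement, not as an error. As written, the chi-square is unstratified and the CMH has no named strata; no sentence calls the CMH unstratified, but nothing in either document supplies strata for it. If the randomisation strata predict CGI, the tests are conservative and somewhat less efficient.

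The size is modest: about 0.6, 1.4 or 2.8 power points at an assumed R² of 2%, 5% or 10% from an illustrative 80%. In the simulation the row-mean-score gain ranges from none to just under 5 points, the latter only at the strongest shift considered. For any improvement it is under 1 point up to s = 0.4 and about 3 points at s = 0.6. These figures rest on assumed strengths of association, an assumed CGI distribution and balance within strata; the documents give none of these for CGI. The primary analysis, the step-down procedure and the sample size are untouched.

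**What to change.** In SAP 15.2.1.4:

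- Run the row-mean-score CMH for each active arm against placebo, stratified by the four randomisation cells as recorded on the RAND eCRF (TRSS <16/≥16 × asthma present/absent).
- Replace the chi-square for each derived category with a CMH test using the same strata.
- State that a missing RAND value is filled from the BAE eDiary mean TRSS or the Asthma Diagnosis eCRF. This rule is needed because SAP 9 and 10 allow for a missing category.
- Cite the <16/≥16 definition in Protocol 5.7 and SAP 9. The text of Protocol 4.0 shows cut-offs that overlap at 16, so the strata need one definition.

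The cost is a few lines of SAP text and two stratification variables in each test's code, plus the missing-stratum rule. No new data and no extra subjects are needed. If the sponsor prefers unstratified tests, one sentence saying so would at least remove the ambiguity, but would forgo the gain.

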#### 15.2.1.5. Proportion of Well Days

A well day is defined as any day where a subject has no moderate or severe RSS without the use of rescue medication. If any of the 8 RSS or the RMS is missing for a specific day the day is not to be considered as a well day.

The proportion of well days is to be calculated as the sum of days where all 8 RSS are non-missing and less than or equal to 1 and RMS is equal to 0, divided by the total number of days in the relevant assessment period (BAE, PAC1, PAC2 or PAC3) as follows:

- Proportion of well days (%) = Number of well days / Total number of days in the relevant assessment period \* 100
- The total number of days in each assessment period (denominator) refers to the total number of days with complete RSS and RMS as required to define a well day.

##### Analysis of Proportion of Well Days

A point estimate and two-sided 95% confidence interval for the difference in adjusted means between the active treatment groups and placebo is to be calculated using the same MMRM as described in Section 15.1.3 Primary Analysis of Primary Efficacy Variable.

The treatment difference corresponding to the mean proportion of symptom free days of the PAC1, PAC2 and PAC3 periods is to be utilised for the secondary analysis.

Observed and change from Baseline values are to be summarised by descriptive statistics for the PAC1, PAC2 and PAC3 periods by treatment group.

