**DATE 01 APRIL 2015** 

The CS is a composite measurement of symptoms as measured by the TRSS and RMS, as measured using a pre-defined rating system that takes into account the different potency of available rescue medication.

The TRSS comprises assessment of 8 symptoms that are given a score of between 0 and 3 giving a range of potential scores of 0 to 24.

Allergy rescue medications will be provided to subjects to be used according to a prespecified Rescue Medication Plan (See Appendix 3). Subjects will be requested to use antihistamine eye drops as first line allergy rescue medication for troublesome ocular symptoms; with oral antihistamines and/or intranasal corticosteroids to be added or substituted if subjects have unacceptable nasal symptoms or ocular antihistamines do not provide adequate symptom relief (see Section 5.8.1). Oral corticosteroids may be prescribed at the Investigator's discretion. The use of allergy rescue medications will be scored based on Didier et al (Didier 2009) as follows:

- RMS = 0; no allergy rescue medication used per day
- RMS = 0.5; at least one dose of antihistamine eye drops used per day
- RMS = 1; at least one dose of oral antihistamine used per day
- RMS = 2; at least one dose of intranasal corticosteroid used per day
- RMS = 3; at least one dose of systemic corticosteroid used per day

The RMS score is not additive, and therefore the maximum RMS is 3. The TRSS (0-24) and the RMS (0-3) will be combined for analysis of the primary endpoint as follows:

$$CS = TRSS/8 + RMS$$

The maximum Combined Score is therefore 6.

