### Additional Inclusion Criteria at End of BAE

- 9. Mean TRSS ≥12 from 4 nasal and 4 non-nasal symptoms during the BAE period (3-week period before randomisation).
- 10. Completed the eDiary during the BAE on at least 16 days (>75% of occasions).

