## 7. STATISTICAL CONSIDERATIONS

### 7.1. ADJUSTMENTS FOR COVARIATES AND FACTORS TO BE INCLUDED IN EFFICACY ANALYSES

The following covariates and factors are to be used in the analyses. For details of their inclusion in the models, see the specific analysis section.

- Study period
  - PAC1
  - PAC2
  - PAC3
- Pooled region as finalised prior to the analysis during the BDR meeting
  - Pooled Region 01
  - Pooled Region 02
  - Pooled Region 03
  - Pooled Region 04
  - Pooled Region 05
  - Pooled Region 06
  - Pooled Region 07
  - Pooled Region 08
- Gender as captured on the Demographics eCRF (DEM)
  - Male
  - Female
- Asthma status as captured on the Asthma Diagnosis eCRF (ASTHMASCR)
  - No asthma
  - Controlled
  - Partly/Uncontrolled
- Baseline score
  - Represents the Baseline value of the relevant score being analysed from the BAE period

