### **15.1.3. PRIMARY ANALYSIS OF PRIMARY EFFICACY VARIABLE**

The primary objective of this study is to test the hypothesis that there is no significant difference in adjusted mean CS between the active HDM-SPIRE treatment groups and placebo.

The null and alternative hypothesis is given by:

$$H_0: \mu_A = \mu_P$$

$$H_1: \mu_A \neq \mu_P$$

Where  $\mu_A$  is the adjusted mean for the active treatment groups and  $\mu_P$  is the adjusted mean for the placebo treatment group.

A point estimate and two-sided 95% confidence interval for the difference in adjusted mean between the active treatment groups and placebo is to be calculated using a Mixed Model Repeated Measures (MMRM) analysis for the PAC1, PAC2 and PAC3 period mean CS.

The MMRM is to include treatment, period and pooled region as main effects, gender, asthma status and Baseline CS as covariate, treatment-by-period and baseline-by-period interaction. An unstructured covariance matrix is to be used to assess within-subject dependence of the 3 observations (PAC1, PAC2 and PAC3) of mean CS per subject.

The following SAS® code is to be used:

---

Document: TH005 SAP Version 2.docx  
Author: [name]

Version Number: 2.0  
Version Date: 24MAR2017

Template No: CS\_TP\_BS016 – Revision 3  
Effective Date: 01May2012

Reference: CS\_WI\_BS005

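### The well-days model most naturally adjusts for a baseline well-day share that the entry rule compresses towards zero; adding baseline CS would recover a modest amount of precision

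*SAP*

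**What the plan says.** SAP 15.2.1.5 counts as well days those on which "all 8 RSS are non-missing and less than or equal to 1 and RMS is equal to 0", divides by the days with complete data, and derives the proportion for the BAE and for each PAC period. Treatment comparisons are made "using the same MMRM as described in Section 15.1.3 Primary Analysis of Primary Efficacy Variable".

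Two places bear on which baseline enters that model:

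- SAP 7.1 lists a baseline score among the covariates and explains it thus: "Represents the Baseline value of the relevant score being analysed from the BAE period". It also refers the reader to each analysis section for details.
- SAP 15.1.3 specifies "gender, asthma status and Baseline CS as covariate, treatment-by-period and baseline-by-period interaction". Its code uses a variable named only `baseline`. Protocol 7.5.3.2.4 applies the primary model to this endpoint, and protocol 7.5.3.1.1 puts the BAE CS in that model.

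Eligibility at the end of the BAE requires "Mean TRSS ≥12 from 4 nasal and 4 non-nasal symptoms during the BAE period" (protocol 4.2). Randomisation is stratified by asthma and by mean BAE TRSS below 16 or at least 16 (protocol 5.7). The TRSS stratum is not a term in the model.

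**The concern.** The entry rule and the well-day definition act on the same diary days and pull in opposite directions. Subjects are selected for a high mean symptom score, and the covariate is then the share of days with a low one. Selection squeezes that share against its floor, and a covariate with little spread can explain little of the outcome.

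For CS, TRSS and the TRSS components, using the score's own baseline keeps a usable measure of severity in the model. For well days it does not do so to the same degree, and the substitution also removes baseline CS, the only severity term in the primary model. Gender, asthma status and pooled region remain.

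What is at stake is the width of the confidence interval for a secondary endpoint. There is also a specification question: two programmers could reasonably fit different models from the present text.

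**Working it through.** **The plan's own figure.** The documents give no power, baseline mean or variability for well days. The only sample-size figure is for CS: difference 0.32, SD 0.986, two-sided 5%, 80% power. It reproduces: 2 × (1.960 + 0.842)² × 0.986² / 0.32² ≈ 149.04, rounded up to 150 per group. It does not bear on this endpoint.

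**Step 1: which baseline.** SAP 7.1 says the BAE value of the score analysed. SAP 15.2.1.5 derives a BAE well-day share and summarises change from it. Together these favour the BAE share. The literal words of SAP 15.1.3 and protocol 7.5.3.1.1 point to baseline CS. For RQLQ the SAP names the covariate explicitly; for well days it does not.

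**Step 2: what entry implies exactly.** On a well day all eight symptoms are at most 1, so TRSS ≤ 8. TRSS runs from 0 to 24 (protocol 3.2.1). If a share w of BAE days are well days and the remaining days reach at most M, the mean TRSS is at most 8w + M(1 − w). A mean of m therefore requires w ≤ (M − m)/(M − 8).

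| Mean BAE TRSS m | M = 24 | M = 18 |
|---|---|---|
| 12 | 12/16 = 75% | 6/10 = 60% |
| 14 | 10/16 = 62.5% | 4/10 = 40% |
| 16 | 8/16 = 50% | 2/10 = 20% |

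Entry lowers the share but does not force it to zero. At the threshold, 0.75 × 21 = 15.75, so up to 15 of 21 days could be well days if every other day were close to the maximum score. That pattern is implausible but not excluded.

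**Step 3: how low in practice.** This depends on within-subject day-to-day variation, which the documents do not give, so diaries were simulated over a range. The assumptions were:

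- eight items rounded to 0-3 over 21 days;
- subject mean TRSS 15 with SD 4 before selection, and entry at a mean of at least 12, which leaves a mean of about 16;
- stable item offsets with SD 0.3 or 0.6;
- rescue use on 0% or 30% of days;
- an average fall of 5 TRSS points by PAC3, with SD 4.

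These levels are of the order of the baseline TRSS in protocol Table 1 (means 15.5-16.4, SD 3.6-5.0), which comes from a chamber challenge, not the field. R² is the share of variance in the PAC3 well-day proportion explained by a single baseline.

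| Within-subject SD of daily TRSS | Mean baseline share | Subjects at exactly 0 | R², baseline share | R², baseline TRSS |
|---|---|---|---|---|
| about 2 | 0.0-0.2% | 95-99% | 1.0-2.7% | 12.0-18.3% |
| about 3.6 | 0.6-2.4% | 67-89% | 5.5-9.5% | 15.1-22.3% |
| about 5 | 2.5-6.7% | 35-65% | 9.2-12.7% | 16.5-22.5% |
| about 6 | 4.9-11.4% | 15-42% | 7.9-13.7% | 16.4-20.2% |

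The baseline share was the weaker predictor in all 16 scenarios.

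**Step 4: what a severity term adds.** A model with both baselines explains at least as much as the better one alone. Adding TRSS to the share therefore cuts residual variance by at least (R²_TRSS − R²_share)/(1 − R²_share). The largest of these lower bounds is (0.181 − 0.015)/0.985 = 16.9%, and the smallest is (0.176 − 0.137)/0.863 = 4.5%.

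Runs with CS itself gave the same direction. Over 16 scenarios with 18-94% of subjects at exactly zero, baseline CS always predicted better than the share, and adding it cut residual variance by 1-17%. A narrower set of assumptions gave 3-11%.

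**Step 5: in terms of interval width.** Width scales with the square root of residual variance: 1 − √0.99 = 0.5% and 1 − √0.83 = 8.9%. The equivalent gain in sample size is 1/0.99 − 1 ≈ 1% to 1/0.83 − 1 ≈ 20%.

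**The case against.** The strongest reply is that the plan may already do what is asked. SAP 7.1 defers to the analysis sections, the well-days section points to 15.1.3, and 15.1.3 names baseline CS, as does the protocol's primary model. On that literal reading baseline CS is already in the model. This stands as a reason not to call the matter settled. It leaves 7.1 and 15.1.3 pointing to different covariates, which an explicit statement would resolve.

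Second, a reader might infer that the entry rule leaves the baseline share at or near zero, so that the endpoint gets almost no baseline adjustment. The documents do not support that. The ceiling at the threshold is 75% of days, and under high day-to-day variation most simulated subjects had some baseline well days and the share explained up to about 14% of the outcome. Only the low-variability scenarios fit the stronger description.

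Third, a reader might infer that severity imbalance between arms goes uncontrolled. Randomisation is stratified on mean BAE TRSS, which limits gross imbalance even though the stratum is not modelled. No bias or type I error problem is shown.

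Fourth, adjusting each score for its own baseline is a consistent rule, and well days lies outside the step-down procedure for the primary analysis. Both points are fair. They keep this minor, and they favour adding CS to the share over replacing the share.

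**Conclusion.** The point holds as a small, avoidable loss of precision combined with an unclear specification. On the better reading of SAP 7.1, the well-days model carries a floor-compressed baseline and no CS, TRSS or TRSS-stratum term. That baseline adjusts for severity less well than baseline CS would in every scenario tried.

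The size is roughly 1-17% of residual variance, or about 0.5-9% of interval width. It rests on assumed day-to-day variability, rescue use and change from baseline, none of which the documents give for field diaries. The tabulated R² values are simple linear fits to PAC3 alone, without region, gender, asthma status or the other periods, so the figures indicate the order of the gain in the planned MMRM and do not measure it. Validity is not in question, and no confirmatory claim depends on this endpoint.

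**What to change.** In SAP 15.2.1.5, state that the well-days MMRM includes mean BAE CS and BAE CS-by-period as covariates in addition to the baseline well-day share and its by-period interaction, with all else unchanged. This fixes one model, keeps the own-baseline rule of SAP 7.1, and removes the ambiguity with 15.1.3.

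The cost is one sentence and, with three periods, three further fixed-effect parameters (one main effect and two interaction terms), which is negligible against roughly 600 expected completers (4 × 150). No new data are needed. The change should be made before unblinding, since a choice between covariates made afterwards would be open to challenge.
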